8.1.4 Severity Assessment

For all AEs, severity should be assessed using the National Cancer Institute's (NCI) Common Terminology Criteria for Adverse Events (CTCAE) Version 5.0, published on 27 November 2017, which provides a grading severity scale for each AE term within a system organ class based on the following general guideline:

- **Grade 1** Mild; asymptomatic or mild symptoms; clinical or diagnostic observations only; intervention not indicated.
- **Grade 2** Moderate; minimal, local or noninvasive intervention indicated; limiting age-appropriate instrumental activities of daily living (ADL)*.
- **Grade 3** Severe or medically significant but not immediately life threatening; hospitalization or prolongation of hospitalization indicated; disabling; limiting self-care ADL**.

- **Grade 4** Life-threatening consequences; urgent intervention indicated.
- **Grade 5** Death related to AE.

*Instrumental ADL refers to preparing meals, shopping for groceries or clothes, using the telephone, managing money, etc.

**Self-care ADL refers to bathing, dressing and undressing, feeding self, using the toilet, taking medications, and not bedridden.

The severity grade as listed by AE term and system organ class in the NCI CTCAE Version 5.0 should be used to define the severity for each AE observed.

(https://ctep.cancer.gov/protocoldevelopment/electronic_applications/ctc.htm).

8.1.5 Causality Assessment

The investigator will assess and document the causal relationship between the study treatment and each AE by answering the question “Do you consider that there is a reasonable possibility that the event may have been caused by the study treatment?”

A reasonable possibility of a relationship conveys that there are facts, evidence, and/or arguments to suggest a causal relationship, rather than a relationship that cannot be ruled out.

An answer of “yes” indicates that there is a reasonable suspicion that the AE is associated with the use of the study treatment.

An assessment of “no” indicates that there is non-plausibility or the existence of a clear alternative explanation.

Factors to be considered in assessing the reasonable possibility of a relationship of the AE to study treatment include:

- Time Course. Exposure to study treatment. Has the participant actually received the investigational product? Did the AE occur in a reasonable temporal relationship to the administration of the study treatment?
- Consistency with the known drug profile. Was the AE consistent with the previous knowledge of the investigational product (pharmacology and toxicology) or drugs of the same pharmacological class? Or could the AE be anticipated from its pharmacological properties?
- De-challenge experience. Did the AE resolve or improve on stopping or reducing the dose of the study treatment?
- No alternative cause. The AE cannot be reasonably explained by another etiology such as the underlying disease, other drugs, other host, or environmental factors.
- Re-challenge experience. Did the AE reoccur if the study treatment was reintroduced after having been stopped? (Note: The Sponsor would not normally recommend or support a re-challenge.)

- Laboratory tests. A specific laboratory investigation (if performed) has confirmed the relationship.
- In difficult cases, other factors could be considered such as: Is this a recognized feature of overdose of the investigational product? Is there a known mechanism?

SAEs will be reviewed by the Sponsor medical monitors and physicians, and further queries will be issued if necessary. The assessment of whether there is a reasonable possibility of a causal relationship is usually made by the investigator. The causality assessment given by the investigator should not be downgraded by the Sponsor. If the Sponsor disagrees with the investigator's causality assessment, the opinion of both the investigator and the Sponsor should be provided with the report.

8.2 Method of Detecting and Collecting Adverse Events

Care will be taken not to introduce bias when detecting AEs and/or SAEs. Open-ended and nonleading verbal questioning of the participant is the preferred method to inquire about AE occurrences.

All AEs spontaneously reported by the participant or reported in response to the open question from the study site staff: "Have you had any health problems since the previous visit/you were last asked?" or revealed by observation will be collected and recorded in the eCRF.

8.2.1 Time Period and Frequency for Collecting Adverse Events

The follow-up period is defined as up to Day 169/EOS. All AEs/SAEs will be collected from the time the participant signs the ICF. After the follow-up period, any SAE that is related to study treatment by investigator assessment should be reported directly to the Sponsor's pharmacovigilance team.

8.2.2 Follow-up of Adverse Events

After the initial AE report, the investigator is required to proactively follow each participant at subsequent visits/contacts. All SAEs will be followed until resolution, stabilization, the event is otherwise explained, or the participant is lost to follow-up.

Any AE that is unresolved at the participant's last study visit will be followed by the investigator for as long as medically indicated (this may be beyond the follow-up period), but without further recording in the eCRF. The Sponsor retains the right to request additional information for any participant with any ongoing AEs at the end of the study, if judged necessary.

8.2.3 Adverse Events Based on Laboratory Test and Examination

Safety assessments, including protocol mandatory laboratory tests, ECG, vital signs, and physical examination, as specified in [Section 7.2](#), will be collected and summarized in the clinical study report by worsening shift change from the baseline value. With this objective way of safety analysis, AE reporting based on examinations and laboratory tests by the investigator should well consider the baseline value and the dynamic changes over time.

8.2.3.1 Laboratory Abnormality

A laboratory test result (including vital signs, ECG, etc.) must be reported as an AE if it meets any of the following criteria:

- Results in a change in study treatment (e.g., treatment interruption or treatment discontinuation)
- Leads to medical intervention (e.g., potassium supplementation for hypokalemia)
- Is clinically significant in the investigator's judgment

It is the investigator's responsibility to review all laboratory findings and to document his/her assessment for abnormal laboratory findings. Medical and scientific judgment should be exercised in deciding whether an isolated laboratory abnormality should be classified as an AE. The AEs relevant to abnormal laboratory values should be followed up till resolution, stabilization (e.g., to baseline value) or an explanation is available, or the participant is lost to follow-up.

Abnormality of a laboratory value, which is unequivocally due to natural disease progression, should not be reported as an AE.

If deterioration in a laboratory value/vital sign is associated with clinical signs and symptoms, the sign or symptom will be reported as an AE, and the associated laboratory result/vital sign will be considered as additional information. Wherever possible the reporting investigator uses the clinical, rather than the laboratory term (e.g., anemia versus low hemoglobin value).

8.2.3.2 Physical examination

Any new or aggravated clinically relevant abnormal medical finding at a physical examination as compared with the Baseline assessment will be reported as an AE unless unequivocally related to the disease under study.

8.3 Expedited Safety Reporting

Investigators must fill the SAE report form and other safety report form (e.g., pregnancy report) provided by the Sponsor and report these events to the pharmacovigilance safety database of the Sponsor immediately (within 24 hours of becoming aware of the event), regardless of relationship to the study treatment.

The investigator will submit any updated SAE information to the Sponsor within 24 hours of it being available. For fatal or life-threatening SAEs where important or relevant information is missing, active follow-up is undertaken immediately. Investigators or other site personnel are required to respond urgent queries immediately but no later than 24 hours of when he or she receives the queries.

Training of SAE reporting will be provided by the Sponsor for each study.

The Sponsor assumes responsibility for expedited reporting of SUSARs to the regulatory authorities and the EudraVigilance database. The Sponsor will also report all SUSARs to the investigator and the head of the investigational institute where required. The investigator (or Sponsor where required) must report SUSARs to the appropriate IEC/IRB that approved the protocol unless otherwise required and documented by the IEC/IRB.

8.4 Pregnancy Report

All pregnancy events must be reported in the period starting from the first dose until 6 months after the last dose of study treatment. The pregnancy itself is not considered to be an AE or SAE, while if the pregnancy outcome meets the criteria for an SAE (i.e., ectopic pregnancy, spontaneous abortion, intrauterine fetal demise, neonatal death, or congenital anomaly), the investigator should follow the procedures for reporting SAEs as specified in [Section 8.3](#).

If a female participant becomes pregnant during the study, the investigator must report the pregnancy to the Sponsor within 24 hours of awareness using the Pregnancy Report/Follow-up Form, and to the relevant institutions in a timely manner per local requirement.

The investigator should follow up on the pregnancy outcome (e.g., any early termination of pregnancy, or a live birth) until 4 weeks after delivery and notify the Sponsor and the EC (or other organizations as required by local regulations) of the pregnancy outcome.

If a male participant's partner becomes pregnant during the clinical study, the investigator must report the pregnancy to the Sponsor within 24 hours of learning of the pregnancy and submit the completed Pregnancy Report/Follow-Up Form. Consent should be obtained from the male participant's partner prior to obtaining any pregnancy result and outcome.

Any poststudy pregnancy-related SAE considered reasonably related to the study intervention by the investigator will be reported to the pharmacovigilance team of the Sponsor.

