5.1 Inclusion Criteria

Participants must fulfil all of the following inclusion criteria for entry into the study:

- 1) Male or female aged ≥ 18 and < 75 years.
- 2) Able to participate and comply with all study procedures and restrictions, and willing to provide written informed consent to participate in the study.
- 3) Diagnosed with AD for [REDACTED], according to the American Academy of Dermatology Consensus diagnostic criteria ([Eichenfield et al. 2014](#)) at the Screening visit.
- 4) Moderate-to-severe AD, defined as:

- a) EASI score ≥ 12 at the Screening visit and ≥ 16 at the Baseline visit
- b) IGA ≥ 3 at the Screening visit and the Baseline visit
- c) BSA $\geq 10\%$ at the Screening visit and the Baseline visit

5) Documented history of inadequate response or lack of tolerability, as assessed by the investigator, to a stable regimen (≥ 4 weeks) of one or more topical treatment, e.g., TCS or TCI before the Screening visit, or for whom topical treatments are otherwise inadvisable.

6) Agree to apply a stable dose of a non-medicated emollient (moisturizer) twice daily at least one week before the Baseline visit and throughout the study.

7) Female participants who are not pregnant or breastfeeding and meet at least one of the following conditions:

- a) Not of childbearing potential as described in [Section 5.3](#).
- b) Of childbearing potential and agrees to use a highly effective method of contraception as described in [Section 5.3](#) consistently from signing of informed consent until 6 months after the last dose of study treatment. Contraception requirements do not apply to participants in an exclusively same-sex relationship. Female participants should not donate eggs until 6 months after the last dose of study treatment.

8) Male participants must be surgically sterilized (performed at least 6 months prior to Baseline [Day 1] visit and documented to no longer produce sperm); or from signing of informed consent until at least 6 months after the last dose of study treatment, agree to use highly effective methods of contraception as described in [Section 5.3](#) with female partners of childbearing potential during the study and must also agree not to donate sperm during this period.

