5.3 Contraception Recommendations

A female who is permanently surgically sterile or postmenopausal is not considered to be a female of childbearing potential and is not required to follow contraception recommendations.

Surgically sterile is defined as:

- Bilateral oophorectomy (surgical removal of both ovaries); or
- Bilateral salpingectomy (surgical removal of both fallopian tubes); or
- Hysterectomy (surgical removal of uterus)

Postmenopausal is defined as no menses for 12 months without an alternative medical cause. A high follicle stimulating hormone level in the postmenopausal range may be used to confirm a postmenopausal state in women not using hormonal contraception or hormonal replacement therapy.

A female who does not meet the definition of postmenopausal or permanently surgically sterile or is postmenarchal or pubertal but has not yet had menses is considered of childbearing potential and is required to practice at least one of the following highly effective methods of birth control consistently from signing of informed consent until 6 months after the last dose of study treatment.

- Combined (containing estrogen and a progestogen) hormonal contraception (oral, intravaginal, transdermal, injectable) associated with the inhibition of ovulation.
- Progestogen-only hormonal contraception (oral, injectable, implantable) associated with inhibition of ovulation.
- Bilateral tubal occlusion/ligation.
- Vasectomized partner(s) provided that the vasectomized partner has received medical confirmation of the surgical success and is the sole sexual partner of the female trial participant of childbearing potential.
- Intrauterine device.
- Intrauterine hormone-releasing system.
- True abstinence (if acceptable per local requirements): Refraining from heterosexual intercourse when this is in line with the preferred and usual lifestyle of the participant. Periodic abstinence

(e.g., using calendar, ovulation, symptothermal, postovulation methods) and withdrawal are not acceptable.

The above-mentioned definition for true abstinence also applies to male participants. Contraception requirements do not apply to participants in an exclusively same-sex relationship.

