6.5 Dose Modifications and Delays

Dose modification of the study treatment is not allowed. Any inadvertent dose modifications should be discussed with the medical monitor. Dosing should occur as close as possible on the allocated visit day and within the visit windows specified in the SoA ([Table 1](#)), except that dosing may be interrupted due to reasons stated in [Section 6.10.1.2](#). If a dose is not administered on schedule due to a visit occurring beyond the visit window specified in the SoA or dose interruption for reasons stated in [Section 6.10.1.2](#), the dose may be administered if it is no later than 5 calendar days after the allocated

visit day (a 10-calendar day delay will be allowed for the last dose at Week 4) specified in the SoA. Otherwise, the dose will be considered missed, and dosing will resume with the next scheduled dose per the SoA.

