7.1.5 End of Study

The EOS visit will be on Day 169.

The investigator may discontinue a participant's study participation at any time during the study when the participant meets the study treatment discontinuation criteria described in [Section 6.10.1](#). A participant may discontinue his or her participation without giving a reason at any time during the study. Should a participant's participation be discontinued, the primary criterion for termination must be recorded by the investigator.

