7.2.5 Pregnancy Testing

For female participant of childbearing potential, serum human chorionic gonadotropin (hCG) will be tested at the Screening, Baseline (Day 1), Week 2 (Day 15), Week 4 (Day 29) visits, and at selected follow-up visits. In addition, urine hCG test must be performed prior to each dosing visit. Following a negative pregnancy test result at Screening, appropriate contraception must be initiated or continued (for participant already on contraceptives) and maintained until 6 months after the last dose of study treatment.

Serum pregnancy tests will also be performed additionally whenever potential pregnancy is suspected. Additional pregnancy tests may also be undertaken if requested by the IEC or if required by local regulations. In the case of a positive confirmed pregnancy, the pregnancy will be immediately reported to the Sponsor and the participant will be followed up until completion or termination of the pregnancy (see [Section 8.4](#)).

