7.4 Pharmacokinetics and Immunogenicity Assessments

Blood will be collected to describe the IMG-007 PK and immunogenicity profiles as outlined in [Table 5](#).

Participants with signs of any potential immune response to IMG-007 will be closely monitored with clinical evaluations. The PK and ADA samples may be collected at unscheduled visits for further evaluation.

Details concerning handling of PK and ADA serum samples, including labeling and shipping instructions, will be provided in the Laboratory Manual. The actual time each sample was collected will be captured to the nearest minute in the eCRF and recorded in the database.

Samples will be shipped to the laboratory where samples will be analyzed for serum IMG-007 concentrations using a validated method.

Validated screening and confirmatory assays will be employed to detect ADAs at multiple timepoints throughout the study.

The immunogenicity evaluation will utilize a risk-based immunogenicity strategy ([Bai et al. 2012](#); [Rosenberg et al. 2004](#)) to characterize ADA responses to IMG-007 in support of the clinical development program.

Table 5 PK and ADA Sampling Schema

Dose No.	Day	Pre-dose /Post-dose	PK blood sampling time	ADA sampling time	Sampling Window
1	1	Pre-dose	0 (pre-dose)	0 (pre-dose)	- 2 hours
	1	Post-dose	EOI	--	+10 mins
	8	Post-dose	7 days post-dose	--	± 3 days
2	15	Pre-dose	0 (pre-dose)	0 (pre-dose)	- 2 hours
	15	Post-dose	EOI	--	+10 mins
3	29	Pre-dose	0 (pre-dose)	0 (pre-dose)	- 2 hours
	29	Post-dose	EOI	--	+10 mins
	43	Post-dose	14 days post-dose	14 days post-dose	± 3 days
57	Post-dose	28 days post-dose	28 days post-dose	± 3 days	
	85/EOT	56 days post-dose	56 days post-dose	± 3 days	
113	Post-dose	84 days post-dose	84 days post-dose	± 3 days	
141	Post-dose	112 days post-dose	112 days post-dose	± 3 days	
169/EOS	Post-dose	140 days post-dose	140 days post-dose	± 3 days	

Abbreviations: ADA = anti-drug antibody; EOI = end of Infusion; EOT = end of treatment; EOS = end of study; PK = pharmacokinetic

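### No scheduled visit, test or call covers about the last six weeks of the 6-month pregnancy-reporting window in protocol Section 8.4

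*Protocol*

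**What the plan says.** Section 8.4 of the protocol sets the reporting window: "All pregnancy events must be reported in the period starting from the first dose until 6 months after the last dose of study treatment". The contraception requirements run to the same point for women (Section 5.3: "birth control consistently from signing of informed consent until 6 months after the last dose of study treatment"; Section 7.2.5: "maintained until 6 months after the last dose of study treatment") and to at least that point for men (Section 5.1: "from signing of informed consent until at least 6 months after the last dose of study treatment").

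The schedule stops sooner. Section 6.4 puts the third and last infusion on Day 29, and Section 6.5 adds that "a 10-calendar day delay will be allowed for the last dose at Week 4". Section 7.1.5 states that "The EOS visit will be on Day 169", and Section 8.2.1 ends the follow-up period there. Table 5 places that visit at "140 days post-dose". The last serum pregnancy test in Table 1 is at Week 24, and SAP Appendix 12.6 gives it an analysis window of Days 149 to 172. The only scheduled telephone contacts are those about 24 hours after each infusion (Section 4.1).

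For partners of male participants, the later part of Section 8.4 is worded differently from its first sentence: "partner becomes pregnant during the clinical study, the investigator must report the pregnancy to the Sponsor within 24 hours". The paragraph on female participants is likewise tied to pregnancies arising during the study.

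**The concern.** The protocol defines a period in which every pregnancy has to be reported, but its schedule gives the site no planned occasion to learn of one in the closing weeks. The 24-hour clock starts when the investigator becomes aware, and extra testing starts when pregnancy is suspected. After Day 169 nothing scheduled would produce either. Partner pregnancies depend on asking or being told throughout, because no test applies to them.

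The routes that continue after follow-up do not fill the gap. Section 8.2.1 asks for related SAEs after the follow-up period, and the last paragraph of Section 8.4 asks for related pregnancy SAEs after the study. Section 8.4 also says that pregnancy in itself is neither an AE nor an SAE, so an uncomplicated pregnancy falls outside both routes. At stake is the completeness of pregnancy safety information in a trial whose primary objective is safety.

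**Working it through.** The check is calendar arithmetic.

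**Inputs.** Last scheduled dose Day 29 (Section 6.4); permitted last dose up to 29 + 10 = Day 39 (Section 6.5); last scheduled visit Day 169 (Section 7.1.5) with a window of ± 3 days (Table 1); reporting window of 6 months from the last dose (Section 8.4). The documents do not convert 6 months to days. I take 183 days, with 180 to 184 as the range.

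**The plan's own figure.** 169 − 29 = 140 days, which agrees with Table 5.

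**The gap.** Window end = last-dose day + 183. Gap = window end − 169.

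- Last dose Day 29: 29 + 183 = Day 212; 212 − 169 = 43 days, or 6.1 weeks; 43/183 is roughly 23% of the six months. With 180 to 184 days the gap is 40 to 44 days.
- Last dose Day 39: 39 + 183 = Day 222; 222 − 169 = 53 days.
- Dosing stopped after Day 15: 15 + 183 − 169 = 29 days.
- Dosing stopped after Day 1: 1 + 183 − 169 = 15 days.
- Day 29 dose with the last visit at Day 172 or Day 166: 212 − 172 = 40 days, or 212 − 166 = 46 days.

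The gap is above zero in every case.

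**Early leavers.** A participant who withdraws before Week 12 has one visit at withdrawal (Section 6.10.2). As an illustration, with a Day 29 dose and withdrawal at Day 43 the period without scheduled contact is 212 − 43 = 169 days. Someone who only stops treatment keeps all remaining visits (Section 6.10.1.1), so this longer gap does not apply to them.

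**Dates.** Enrolment ran from 18 July 2023 to 31 January 2024 (Section 4.1). Assume the last participant had Day 1 on 31 January 2024 and stayed on schedule. Day 29 is then 28 February, Day 169 is 17 July and the six-month point is 28 August 2024, which is 42 days after the last visit. Both later dates follow the protocol date of 14 June 2024. On the same schedule, a participant with Day 1 on 16 November 2023 had Day 29 on 14 December 2023 and reached six months on 14 June 2024. Earlier enrollees had already passed that point when the current protocol was dated.

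**The case against.** A reader might infer that pregnancies after Day 169 go wholly unascertained. The documents do not support that. The first sentence of Section 8.4 keeps the duty in force to six months. Section 8.3 requires the pregnancy form within 24 hours of awareness, without limiting this to the study period. Section 7.2.5 calls for a serum test whenever pregnancy is suspected and gives no end date. What is missing is scheduled, active ascertainment.

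A reader might also infer that the later paragraphs of Section 8.4 cut the duty back to each participant's own Day 169. That reading is weak. Those paragraphs can be taken as giving form and timing for a duty already stated in full, and Section 8.3 applies regardless. Section 4.2 also defines the study period for the trial as a whole, ending with the last participant. On the assumed dates the trial ends on 17 July 2024, so anyone last dosed by 17 January 2024 (Day 1 by 20 December 2023, on schedule) has the full six months inside the study period. The difference in wording then matters only for later enrollees, whose number is not given. It is still worth removing, but it does not revoke the first sentence.

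Nor can it be said that a pregnancy statement in the study report would be wrong. Neither document plans one over a defined window; SAP Section 6.9.2 provides only a listing of pregnancy tests.

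Two further points stand. The consent form is not among the available documents, so participants may be told to notify the site after the last visit. The reach is also small: 13 participants were enrolled, the number of childbearing potential is not stated, and those who withdraw consent cannot be contacted.

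**Conclusion.** The point holds as a mismatch between the reporting window and the schedule. For a participant dosed through Day 29, about 43 days of the six months after the last dose have no scheduled visit, test or call. The figure is about 53 days with the latest permitted last dose, 29 or 15 days if dosing stopped at Day 15 or Day 1, and more for those who leave the study before Week 12. In that period the duty to report remains, but as scheduled, detection relies on spontaneous reporting.

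This rests on six months being about 183 days and on no contact being arranged in documents not seen here. No endpoint or planned analysis is affected. With at most 13 participants this is a modest, inexpensive improvement. Which window length is right is for the sponsor to settle; the passages need to be reconciled with each other.

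**What to change.** Reconcile the reporting window in Section 8.4 with Table 1. Then:

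- Add one remote pregnancy-status contact to Table 1 at the end of whichever window the sponsor retains, counted from each participant's actual last dose. A telephone call would do, as the protocol already uses them after infusions.
- Put the question to women of childbearing potential, and to male participants about their partners. Include people who left the study early without withdrawing consent. Participants whose window has already closed can be asked retrospectively.
- Word the later paragraphs of Section 8.4, for female participants and for partners, to cover the same window as its first sentence.

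The cost is one contact for at most 13 participants and a short amendment, which needs IRB/IEC approval before use (Sections 12.1 and 12.2). If the six-month window is kept, pregnancy status closes about six weeks after the last visit for a participant dosed on schedule. The Day 169 database need not wait for it.
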